Values are Mean ± SD; eCPAP= extended CPAP; CGA= corrected gestational age; RND= randomization; Avg=Average; *p<0.05 for the difference in the change in FRC between the CPAP and no CPAP infants by multiple linear regression with repeated measures and time treatment interaction adjusting for gender, twins, and weight at randomization.

Extended CPAP may constrain developmental therapies⁷⁷ and may affect intermittent hypoxic episodes which are common in preterm infants, underestimated by clinically used pulse oximeter settings, but have been associated with long-term neurodevelopmental problems⁷⁸⁻⁸⁰. The pilot eCPAP study had limited funding for the collection of detailed clinical respiratory and neurodevelopmental outcomes after discharge from the NICU. These outcomes will be explored in greater detail in the proposed study to provide data for a planned multicenter trial. In the pilot eCPAP study, 89% of the infants had a respiratory questionnaire done at 12 months of age with wheeze or cough without cold as per parent report³⁵ occurring in 58% of the infants in the eCPAP arm versus 73% in the CPAP discontinuation. This will be further studied with monthly respiratory questionnaires in the proposed study. Available Bayley neurodevelopmental scores at 6 months CGA from 29 of the 44 infants in the pilot study demonstrated the infants in the eCPAP arm had an average cognitive percentile score of 61.5% versus 46.7% in the CPAP discontinuation arm.

b3d. Sedation with Chloral Hydrate

Sedation with chloral hydrate is the standard for infant PFTs after 44 weeks of CGA as per the American Thoracic Society^{81;82}. [name] has IRB approval for sedation for PFTs at Oregon Health & Science University (OHSU) for term/preterm infants (current eIRB #386). In our recent RCT (Drs. [name], [name] Co-Pls; [name]) "Vitamin C to Decrease the Effects of Smoking in Pregnancy on Infant Lung Function (VCSIP)^{83;84}, chloral hydrate sedation was done in 220 infants at 3 and 12 months of age for a total of about 440 total pulmonary function tests. There were no serious adverse events due to sedation.

3. Rationale for a Randomized Clinical Trial

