Infant pulmonary function testing will be performed when CPAP stability criteria is met prior to randomization and at the end of the two week treatment period. Studies will be performed with the infant supine, quietly asleep and at least 30 minutes after a feed. All measurements will be obtained using a computerized infant pulmonary function cart (SensorMedics 2600; SensorMedics Inc, Yorba Linda, CA; Jaeger/Viasys Master Screen Baby Body) in the OHSU NICU at the infant's bedside. Standard testing criteria outlined by the American Thoracic Society / European Respiratory Society will be met ^{81;93,94}. Tidal breathing will be recorded with up to 50 flow-volume loops⁴⁶. Passive respiratory mechanics (respiratory compliance [Crs] and respiratory resistance [Rrs]) will be obtained using the single breath occlusion technique⁹⁵. Functional residual capacity (FRC) will be obtained with the nitrogen washout technique with acceptance criteria as per ATS/ERS guidelines⁹⁴. Vital signs (respiratory rate, heart rate, oxygen saturation) will be continuously monitored during the testing. If a PFT does not meet the pre-specified technically acceptable criteria it can be reattempted in 24-48 hours.

d. Outpatient Infant Pulmonary Function Tests

Infant pulmonary function testing will be performed at 6 months of CGA (range of 5-8 months corrected age) at OHSU for all randomized patients. These will be primarily directed and performed by [name] who will be blinded to the NICU treatment allocation. [name] has experience with measurements of V_A, D_L,

and FEFs as these are the PFTs that were performed in the study at the Oregon National Primate Research Center examining the effect of CPAP on lung development. [name] RRT will also be a part of the research team performing the 6 month PFTs and he will be blinded as well. He was an integral part of the successful VCSIP study^{83,84} which measured FEFs at 3 and 12 months of age in offspring of pregnant smokers randomized to vitamin C versus placebo during pregnancy. Standard acceptance criteria will be applied. The PFT results will be reviewed off site for acceptability, reproducibility, and completeness by [name] and/or [name], RRT who has over ten years of experience in [name] PFT laboratory performing and interpreting these tests. They will be blinded to the treatment allocation in the NICU as will the statisticians at Indiana University performing the data analysis.

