Appendix A

Data Collection Schedule

	Study entry	Beginning of treatment period	After 2 week treatment period	6 months of age	6-12 months of age	Discharge through 12mo of age
Consent and medical history	Х	•				
Breathing test*		X	X	Х		
Blood sample**			Х			
Monthly breathing questionnaire by phone						Х
Neurodevelopmental testing					Х	

^{*}A syrup to make child sleepy will be given only at the 6 month breathing test
** Collected when a sample for clinical care is being done

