Specific Aim 1 (Primary Outcome): General linear mixed models (GLMMs) models will be used to compare the primary outcome of alveolar volume (V_A) between the eCPAP and CPAP discontinuation group while adjusting for gestational age at delivery (randomization stratification variable) and other baseline variables that are found to be statistically different between the two groups. Since the lung function measures are highly dependent on infant length and sex, we will further adjust for length and sex in the GLMMs as indicated. In order to adjust for intra-twin correlations, generalized estimating equations (GEEs) with the linear link function will be used to model V_A . The GLMMs can be performed using the GEE estimation approach. Intention to treat analysis will be used for the primary analysis of all aims.

Specific Aim 2 (Secondary Outcomes): Lung diffusion capacity (DLCO) and forced expiratory flows (FEFs) and specifically FEF $_{50}$ will be analyzed with the same general approaches described for the primary outcome of V_A in Specific Aim 1.

FRC measurements in the NICU done pre and post randomization and FEF₂₅₋₇₅, FEF₇₅ done at 6 months of corrected age will be analyzed with the same general approaches as above in Specific Aim 1.

Specific Aim 3 (Exploratory Outcomes): Logistic regression models will be used to compare the incidence of wheeze and the incidence of wheeze and cough between the two groups adjusting for gestational age at delivery (See appendix for standardized respiratory questionnaire administered). Neurodevelopmental scores will be analyzed with the same general approaches described for the primary outcome of V_A in Specific Aim 1.

Intention to treat analysis will be used for the primary analysis of all aims. In addition, all of the aims will also be analyzed with the same general approach using a per protocol analysis and "as treated analysis".

Sample Size and Power Considerations. No studies have compared V_A at 6 months of age in stable infants randomized to eCPAP versus CPAP discontinuation in the NICU. Data from our pilot eCPAP study showed a 12% higher FRC in infants randomized to eCPAP at the end of two week treatment period¹. A study by [name] et al reported a 16% difference in both V_A and D_L in preterm infants according to CPAP treatment in the NICU (Table 1)² and a 12% difference in D_L between infants with BPD versus healthy term infants³. Therefore,

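### The SAP does not prespecify pre-randomization FRC as a covariate for end-of-treatment FRC, which gives up some precision on a supplementary in-NICU outcome

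*SAP*

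**What the plan says.** Protocol section 6.c says inpatient lung function testing, which includes FRC, "will be performed when CPAP stability criteria is met prior to randomization and at the end of the two week treatment period". Section 4.a gives the same timing.

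The SAP, under Specific Aim 2, names "FRC measurements in the NICU done pre and post randomization" in one sentence with FEF25-75 and FEF75 and says that they "will be analyzed with the same general approaches as above in Specific Aim 1". The Aim 1 model adjusts for gestational age at delivery and for "other baseline variables that are found to be statistically different between the two groups". It adds that "we will further adjust for length and sex in the GLMMs as indicated". Neither place mentions a baseline FRC covariate, a change score or a time-by-treatment term.

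The footnote to pilot Table 2 (Protocol section 2, b3c) describes a different analysis of the same measurement: a test of the "difference in the change in FRC between the CPAP and no CPAP infants by multiple linear regression with repeated measures", with a time-by-treatment interaction.

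**The concern.** Alveolar volume is measured only after discharge, so a model built for it has no place for a baseline value of the outcome. FRC has one. Applied as written, the borrowed model leaves two things open.

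- **The role of the pre-randomization value.** The sentence lists it beside the post-treatment value as something to analyse. A between-arm comparison of a value taken before randomization can show only chance.
- **The model for the end-of-treatment value.** The one stated route by which baseline FRC can enter is a significant between-arm difference. That is a poor rule for a prognostic baseline: the gain in precision comes from its correlation with the outcome, not from imbalance.

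An analyst could run a post-only, change-score, baseline-adjusted or repeated-measures analysis and call each one compliant. The pilot shows that the choice moves the estimate. At stake are the precision and the prespecification of the lung volume measured directly after treatment.

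**Working it through.** **The plan's own figures.** Neither document gives power, an SD at end of treatment or a pre/post correlation for FRC. The nearest figure is the pilot's 12% higher FRC at the end of treatment. Crude means from Table 2 are 40.5 + 12.6 = 53.1 mL and 41.5 + 6.4 = 47.9 mL, and 53.1/47.9 − 1 = 10.9%. The pilot model was adjusted, so the gap from 12% is not in itself an error.

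**The significance rule applied to the pilot.** The baseline means differ by 1.0 mL with SDs of 11.8 and 10.6 and 22 infants per arm: t = 1.0 / (11.22 × √(2/22)) = 0.30, p = 0.77. The rule would not adjust. The crude post-only difference is 53.1 − 47.9 = 5.2 mL, and the difference in change is 12.6 − 6.4 = 6.2 mL. An unremarkable imbalance therefore moves the crude estimate by 1.0/6.2 = 16%, and the SAP does not say which version will be reported.

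**Inputs for the precision check**

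- Baseline SD: √((11.8² + 10.6²)/2) = 11.22 mL (pilot Table 2).
- SD of change to 2 weeks: √((11.4² + 10.1²)/2) = 10.77 mL (pilot Table 2).
- Difference: 6.2 mL (pilot Table 2).
- Infants per arm: 50 × 0.90 = 45 (the SAP's allowance for 10% missing NICU data).
- Alpha: 0.05. Two-sided testing is assumed, because the SAP does not state sidedness.
- End-of-treatment SD, s₂: not reported; assumed 11 to 16 mL.
- Share of FRC variance explained by gestational age, length and sex, R: not reported; assumed 20 to 40% of both measurements.
- Twin correlation is ignored.

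**Step 1, implied correlation.** r = (11.22² + s₂² − 10.77²) / (2 × 11.22 × s₂). At s₂ = 11, r² = 0.28. At 11.2, 13 and 16, r = 0.54, 0.61 and 0.74, so r² = 0.29, 0.38 and 0.55.

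**Step 2, what remains after the SAP's covariates.** The partial correlation is (r − R)/(1 − R). This takes the covariates to act on both measurements through the same combination, which is the assumption least favourable to baseline FRC. The extra share of residual variance removed is the square of that value. For s₂ = 16 and R = 0.20: (0.741 − 0.20)/0.80 = 0.676, squared 0.46.

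**Step 3, power.** The residual SD without baseline FRC is s₂√(1 − R). With it, that is multiplied by √(1 − partial r²). Power is from a two-sample t test with 45 per arm.

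| s₂ (mL) | R | Extra variance removed | Power without baseline FRC | Power with it |
|---|---|---|---|---|
| 11.2 | 20% | 18% | 83% | 89% |
| 11.2 | 40% | 5% | 92% | 93% |
| 13 | 20% | 27% | 71% | 83% |
| 13 | 40% | 13% | 82% | 87% |
| 16 | 20% | 46% | 53% | 79% |
| 16 | 40% | 32% | 65% | 81% |

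With no covariates at all (R = 0), power would be 74%, 61% and 44% without baseline FRC and 87%, 81% and 77% with it. That comparison is not the SAP's model and is shown only as the outer limit.

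**The case against.** The strongest reply is that the SAP is silent rather than contrary. Its Aim 1 approach is a mixed model with GEE estimation for correlated data, and a joint model of the pre and post values fits that wording. The same group used repeated measures in the pilot. This stands: a reader might infer that the SAP has decided to treat baseline FRC as an outcome, and the text does not go that far. What it does not do is settle the choice.

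Other stronger readings also fail.

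- **Large loss of explainable variance.** A reader might take the unadjusted r² of 0.28 to 0.55 as the loss. The SAP model already adjusts for gestational age, length and sex, so the real loss is smaller, and near nothing at the favourable end.
- **Bias.** Randomization protects a post-only comparison, and a significant imbalance would trigger adjustment. Only a non-significant one would go uncorrected.
- **A baseline for every infant.** That is the plan, but the SAP allows 10% missing NICU data, including unsuccessful tests.
- **Timing of the first test.** Appendix A heads its column "Beginning of treatment period", but Protocol sections 4.a and 6.c both place the test before randomization.
- **Purpose of protocol version 2.0.** The amendment history records a clarification of the pre-randomization FRC measurement and gives no reason, so nothing follows from it about the intended analysis.

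It is also fair that FRC is supplementary. The Aim 2 statements name diffusion and forced flows, and no power is claimed for FRC.

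**Conclusion.** The concern holds as a gap in prespecification with a cost in precision. Pre-randomization FRC is collected by design, yet it is not a prespecified covariate for end-of-treatment FRC, and the only stated way in is a chance significant imbalance. Over the assumed ranges, adding it removes about 5 to 46% of the remaining variance and raises power by 1 to 26 percentage points. It lowered power in none of the scenarios. The gain is small if end-of-treatment SD stays near its baseline value and the other covariates explain much of FRC. It is substantial if the SD grows toward 16 mL. The documents do not show which case applies. No bias follows, and the alveolar volume analysis is unaffected.

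**What to change.** Replace the FRC part of the sentence in the SAP's Specific Aim 2 with wording such as:

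> End-of-treatment FRC will be compared between arms with the Aim 1 model plus pre-randomization FRC as a covariate, regardless of any test of baseline difference. If a baseline value is missing, a repeated-measures model with a common baseline mean will be used. Pre-randomization FRC is a baseline characteristic and will not be tested as an outcome.

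The sentence on FEF25-75 and FEF75 can stay as it is. The change should be made before treatment allocations are linked to the FRC data. It costs one sentence of SAP text and needs no new measurements, visits or infants.

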- We anticipate screening 300 infants to recruit the cohort
- Up to 130 infants will be consented once inclusion/exclusion criteria have been verified
- 100 infants will be randomized

b. Inclusion Criteria

- 1) Infants born at >24 to ≤ 32 weeks gestation
- 2) Treated with CPAP for ≥ 24 hours for respiratory distress (either as initial therapy or following extubation)

c. Exclusion Criteria

- 1) Significant congenital heart disease
- 2) Major malformations
- 3) Chromosomal anomalies
- 4) Culture proven sepsis at consent

- 5) Complex maternal medical conditions
- 6) Clinical instability
- 7) Multiple gestations > twins
- 8) <3rd or >97th percentile for weight⁸⁵
- 9) Participating in another neonatal randomized clinical trial with a competing outcome
- **10)** Mother/legal guardian without stable method of communication

Additional criteria that must be met prior to randomization:

- 1) CPAP stability criteria met for at least 12 hours
 - The following CPAP stability criteria 16;86 has to be met for more than 12 hours by 34 weeks of CGA:
 - o CPAP of 5 cmH2O
 - o On room air
 - o Respiratory rate ≤70 bpm without significant retractions
 - <3 self-resolving apneas or bradycardias or desaturations in 1 hour in last 6 hours

 - Average SpO2 >86% for 90% of the last 24 hours
 - Not being treated for a patent ductous or sepsis
 - o Tolerating CPAP "cares"

d. Vulnerable Populations

Neonates will be included in this research. The inclusion of neonates is critical to the research because we have pilot data in preterm infants demonstrating that eCPAP may stimulate lung growth. However, our initial trial did not include follow-up testing after discharge to determine the potential duration of the effect of eCPAP on lung volumes and did not include measurements of lung diffusing capacity. Parent or guardian permission will be obtained before the child will be enrolled in the study, as per IRB guidelines.

e. Setting

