Randomization will be done via REDCap by the data management team within strata defined by gestational age at delivery (28 and 6/7 and 29 and 0/7 weeks). If twins are both enrolled they will be allocated to the same treatment arm⁸⁹. A computer generated randomization scheme with stratum using random block sizes of 2 or 4 will be uploaded into REDCap for retrieval. The NICU team will know the treatment allocation but the follow-up research team assessing outcomes will be blinded to the treatment allocation. The electronic medical record will note the infant was in the study, but will not state allocation arm.

i. Assessment of Treatment Adherence

After randomization, the infant will be assessed daily by research staff for the 14 days on the assigned trial arm. As done in the pilot eCPAP study¹⁶, failure criteria for the respective randomization arms will be as follows: Infants randomized to dCPAP (usual care) will be defined as failing if they demonstrate:

- significantly increased work of breathing with a persistent respiratory rate > 75 breaths/ minute,
- o increased apnea and/or bradycardia and/or desaturations > 2 significant episodes in 1 hour in the past 6 hours,
- o oxygen need to maintain oxygen saturations > 86%,
- o a blood gas pH of < 7.2, PaCO2 > 65 mm Hg, or
- o major apnea or bradycardia needing resuscitation 16;86

Subjects who meet the criteria for failing dCPAP will be resumed on their previous level of CPAP. Another attempt to discontinue the subject's CPAP will occur within the next 5 days when they again meet the predefined stability criteria. If the subject does not meet the stability criteria or fails a second attempt at discontinuation, further weaning/management will be by the clinical team. The infant will continue to be studied as intention to treat. In our pilot study¹⁶, only 1 out of 26 subjects failed CPAP discontinuation.

Infants randomized to the eCPAP arm will have the CPAP stopped during the treatment period if there is significant abdominal distension with feeding intolerance or significant nasal breakdown (checked and documented every 3-4 hours as outlined in the OHSU NICU's CCG). The CPAP will be discontinued for up to 5 days and if symptoms resolve, the CPAP will be reapplied. If symptoms reoccur, the CPAP will be removed and further management will be by the clinical team. The infant will continued to be studied as intention to treat. In the pilot CPAP study¹⁶, all 22 patients tolerated eCPAP without adverse events.

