General linear mixed models (GLMMs) will be used to compare the primary outcomes of alveolar volume (V_A) between the eCPAP and dCPAP while adjusting for the design factor gestational age at delivery (28 and 6/7 and 29 and 0/7 weeks) and other baseline variables that are found to be statistically different between the two groups. Since the lung function measures are highly dependent on infant length and sex, we will further adjust for length and sex in the GLMMs. In order to adjust for intra-twin correlations, generalized Estimating Equations (GEEs) with the linear link function will be used to model $V_{A...}$ The GLMMs can be performed using the GEE estimation approach. Intention to treat analysis will be used for all aims as the primary analysis. The intention to treat population is defined as all randomized infants and the analysis uses the assigned randomization group even if infants did not complete the intervention. In addition, a per protocol analysis will be completed for all aims. The per protocol population is defined as all infants who successfully completed the treatment arm to which they were assigned.

b2. Specific Aim 2 (Secondary Outcomes)

Lung diffusion (D_L) and FEF₅₀ will be will be analyzed with the same general approaches described for the primary outcome in SA #1.

b3. Specific Aim 3 (Exploratory Outcomes)

Logistic regression models will be used to compare the incidence of wheeze and the incidence of wheeze and cough between the two groups adjusting for GA at delivery (<29 vs ≥ 29 weeks). Neurodevelopmental scores will be analyzed with the same general approaches described for the primary outcome in Specific Aim 1.

c. Missing Data

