Completed: All randomized or assigned infants who had not discontinued and had not been

withdrawn.

85 Discontinued: All randomized or assigned infants who were withdrawn by investigator.

87 Alveolar volume

completed: Have a completed procedure with a corrected age of approximately 6 months (allowable

range of 4 - 12 months corrected age).

DLCO completed: Have a completed procedure with a corrected age of approximately 6 months (allowable range of 4 - 12 months corrected age). FEFs completed: Have a completed procedure with a corrected age of approximately 6 months (allowable range of 4 - 14 months corrected age). Clinical Respiratory Outcome Done: Have at least one respiratory questionnaire completed at 4 months of corrected age or

Neurodevelopmental

 Outcome Done: Have a neurodevelopmental exam completed at less than or equal to 16 months of

corrected age.

¹ 2nd twin is assigned to same arm as 1st twin that is randomized

Data Analyses:

- 1) Outcomes data will initially be analyzed by ITT, according to the treatment arm the infants were randomized or assigned to, regardless of treatment adherence. **THIS IS THE PRIMARY ANALYSIS**.
- 2) Outcomes data will secondarily be analyzed by per protocol analyses, that is only the infants who received the intervention as randomized or assigned will be included.
- 3) Outcomes data will be analyzed by "as treated analyses" by the treatment received.

POWER AND STATISTICAL CONSIDERATIONS/ANALYSIS

Statistical Analysis. All outcomes will be analyzed by a statistician blinded to the infants' treatment assignments by intention to treat. Maternal and infant characteristics will be compared using the independent-samples t-test for continuous measures (or the Wilcoxon–Mann–Whitney test for nonnormal distributions) and the chi-square test for categorical variables. We will examine the distributions of continuous variables and use alternative approaches such as transformation or nonparametric methods in cases of violation to the normal distribution assumption. We will examine the frequency distribution of all categorical variables and adopt exact inference procedures in cases of zero or small cell size. All analyses will be conducted using the SAS 9.4 (SAS Institute, Carey, NC).

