we powered our randomized trial to detect a 12% difference in V_A between the eCPAP and CPAP discontinuation groups.

Using ANCOVA model and assuming a mean V_A of 642 mL (SD=189) based on data of the overall mean and SD from the

Table 1. Estimated power for 34 infants per group with completed PFT data

Macan (SD) in _____ Estimated Power for Group Differences

Outcome Measures	Mean (SD) in Control Group	Estimated Power for Group Differences		
		12%	15%	17%
Alveolar volume (V _A)	642 (189)	80	92	97
Lung diffusing capacity (D _L)	4.1 (1.19)	80	92	98
Forced Expiratory Flow (FEF ₅₀)	346 (129)	35	49	60

control and CPAP groups reported in Assaf et al², a sample size of 34 infants per group is needed to yield 80% power for detecting a 12% difference (effect size=0.42) in V_A in the eCPAP group at α =0.05. This sample size also allows us to detect a 12% difference in D_L with an effect size of 0.42. We estimate that 18% of the study patients will be twin pairs based on our pilot eCPAP study. Conservatively counting just one infant out of each twin pair for sample size estimation, we will need 38 infants per group (76 total infants at 6 months) with completed V_A outcomes. We further assume a 10% missing data in the NICU (unsuccessful test or infants transferred to another facility) and a 15% loss from NICU discharge to the 6 month PFT (cohort loss, unacceptable PFT, unsuccessful sedation) and therefore we will need to randomize and/or assign 50 infants per group (total n=100) into the trial. This sample size will provide 80% power for detecting an effect size difference of 0.42 in outcome measures between the two groups in Aim 1 (primary outcome of V_A) and Aim 2 for D_L . This sample size allows us to detect a 23% difference in FEF₅₀.

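### The two Aim 3 wheeze models have no stated handling of twin pairs, although co-twins share an arm and the continuous outcomes are adjusted for this

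*SAP*

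**What the plan says.** **Allocation.** Protocol section 5h states "If twins are both enrolled they will be allocated to the same treatment arm", and the footnote to the SAP's Population section states "2nd twin is assigned to same arm as 1st twin that is randomized". Higher-order multiples are excluded (Protocol 5c: "Multiple gestations > twins"), so no family contributes more than two infants.

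**Continuous outcomes.** For alveolar volume, SAP Specific Aim 1 says "In order to adjust for intra-twin correlations, generalized estimating equations (GEEs) with the linear link function will be used to model" that outcome. Specific Aim 2 applies the Aim 1 approach to DLCO, the forced expiratory flows and FRC. Within Specific Aim 3 the SAP adds "Neurodevelopmental scores will be analyzed with the same general approaches described for the primary outcome of V_A in Specific Aim 1".

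**Wheeze outcomes.** The sentence just before that one in Specific Aim 3 reads "Logistic regression models will be used to compare the incidence of wheeze and the incidence of wheeze and cough between the two groups", with gestational age at delivery as the only named adjustment. Protocol section 7.b3 matches it: the comparison is "between the two groups adjusting for GA at delivery". Neither document names GEE, a random effect, a robust variance or a one-infant-per-pair rule for these two outcomes.

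**Twin share.** SAP, Sample Size and Power Considerations: "We estimate that 18% of the study patients will be twin pairs based on our pilot eCPAP study".

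**The concern.** Pairs sit wholly within one arm, so two correlated answers carry less information about the arm difference than two independent ones. An ordinary logistic regression ignores this and reports standard errors that are too small when the correlation is positive. Positive correlation is plausible, since co-twins share a household and a gestational age. Wheeze is also reported by the child's primary caretaker, although the documents do not say whether one person answers for both twins.

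The plan recognises the problem for every continuous outcome and leaves it open only for the two binary ones. Each of the two is to be analysed by intention to treat, per protocol and as treated, so the gap recurs in six analyses. Aim 3 is meant to supply pilot data for a later multi-center trial, and its intervals may be used for planning. A silent SAP also leaves the analyst to choose the twin handling after the data are in, or to ignore it.

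**Working it through.** **1. Does any other text close the gap?**
- The SAP remark that the mixed models may be estimated by GEE belongs to the linear models of Aim 1.
- The statement that all aims use the same general approach introduces the per protocol and as treated analyses. It repeats each aim's own model and does not add GEE to the logistic one.
- Counting one infant per pair is a step in the alveolar volume sample size, not an analysis rule.
- The provision for exact methods concerns sparse cells.

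None supplies twin handling for wheeze.

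**2. The plan's own twin figure.** The SAP goes from 34 to 38 per group by counting one infant per pair. If 18% of infants are in pairs, 9% are not counted: 34 / 0.91 = 37.4, rounded up to 38. If instead 18% of families were pairs, 34 families would mean 34 × 1.18 = 40.1 infants, which does not match. The first reading is used below.

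**3. The plan's wheeze power** (50 per group less 15% = 42.5; two-sided 5% assumed). The stated 70% for 48% against 21% reproduces in two ways: a pooled test at 38 per group (one infant per pair) gives 70.5%, and Fisher's test at 43 per group (no twin discount) gives 69.9%. The power statement therefore does not show which twin handling was intended. The stated 90% for 79% against 50% reproduces under neither: pooled 76.3% at 38, Fisher 76.2% at 43. Even the pooled test at 43 with no twin discount gives 81.4%, so that shortfall is not a twin effect and is a separate matter.

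**4. Design effect.** With clusters of at most two and a share q = 0.18 of infants in pairs, DE = 1 + q × ICC, and the unadjusted standard error is too small by 1 − 1/√DE.

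| ICC (assumed) | DE | SE too small by |
|---|---|---|
| 0.1 | 1.018 | 0.9% |
| 0.2 | 1.036 | 1.8% |
| 0.3 | 1.054 | 2.6% |
| 0.5 | 1.090 | 4.2% |
| 0.8 | 1.144 | 6.5% |

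Under the family reading, q = 0.36 / 1.18 = 0.305. The shortfall is then 4.3%, 6.9% and 10.3% at ICC 0.3, 0.5 and 0.8.

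**5. Simulation with no true effect.** Each arm has 35 single infants and 4 pairs (43 infants; 86 infants in 78 families overall). The model has arm and gestational age stratum, and the co-twin copies the first twin's outcome with probability ICC. There are 20,000 runs per cell, with Monte Carlo error of about 0.15 to 0.19 points. Rejection at a nominal 5%:

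| Wheeze rate, test | ICC 0 | 0.3 | 0.5 | 0.8 |
|---|---|---|---|---|
| 48%, Wald | 4.7% | 5.6% | 6.3% | 6.7% |
| 48%, likelihood ratio | 5.2% | 6.1% | 6.8% | 7.3% |
| 48%, family-clustered sandwich | 5.0% | 5.3% | 5.6% | 5.3% |
| 79%, Wald | 4.4% | 4.8% | 5.5% | 6.3% |
| 79%, likelihood ratio | 5.3% | 6.1% | 6.7% | 7.6% |
| 79%, family-clustered sandwich | 4.6% | 4.7% | 4.8% | 5.1% |

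Repeats with 40,000 runs per cell at 48% gave Wald rates of 5.4 to 5.5% at ICC 0.3 and 5.8 to 6.1% at 0.5, so differences of a few tenths of a point should not be read closely. The likelihood ratio test already rejects slightly above 5% with no correlation, so not all of its excess comes from twins.

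**6. Interval width.** The mean sandwich standard error divided by the model-based one is 1.022, 1.039 and 1.065 at ICC 0.3, 0.5 and 0.8 for a 48% rate, and 1.020, 1.035 and 1.058 for 79%. This agrees with step 4.

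**The case against.** The strongest reply is that this is silence, not a contradiction. A logistic GEE is a logistic regression model, so the wording permits it, and the same section already commits to handling twin correlation. That is fair: independence is the default reading, not the only one. It is also the reason the SAP should say which is meant.

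The second reply is size. The documents give no within-pair correlation, and up to an ICC of 0.3 the Wald test shows no material excess over 5%. The outcomes are exploratory and no decision rule rests on them. This stands and sets the severity, but it does not make the unadjusted standard errors right.

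Third, the direction is certain only while co-twins are in the same group. In the as treated analysis they could be separated, and positive correlation would then make unadjusted standard errors too large. This also stands, and the claim about direction is limited to analyses by assigned arm. Clustering on family deals with either case.

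Last, the 18% sentence is ambiguous. The reading used here is the one that fits the plan's step from 34 to 38, and it gives the smaller effect.

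**Conclusion.** The point holds and is minor. No text in either document gives twin handling for the two wheeze models, while the continuous outcomes have it. In the intention-to-treat analysis, unadjusted standard errors would be about 1 to 6.5% too small for an assumed ICC of 0.1 to 0.8 with 18% of infants in pairs, or up to about 10% if 18% refers to families. At 18% of infants, the rejection rate of a nominal 5% Wald test stays close to 5% up to ICC 0.3 and reaches at most about 6.7% at 0.8. The size rests on the assumed correlation; the omission does not. The primary alveolar volume test is untouched, and no claim is made that twins make the stated wheeze power too high.

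**What to change.** Add one sentence to SAP Specific Aim 3: both wheeze outcomes will be fitted by GEE with a logit link, clustered on family and adjusted for the gestational age stratum, using a named robust variance estimator, in all three analysis populations. The plain family-clustered sandwich is adequate here: in the simulation it rejected 4.6 to 5.6% of the time across ICC 0 to 0.8. If the wheeze power paragraph is reissued, state its method, sidedness, number per group and twin handling.

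The cost is that sentence and one clustering statement in the SAS code. Design, sample size and data collection do not change. Intervals become about 2% wider at ICC 0.3, 3.5 to 3.9% at 0.5 and 5.8 to 6.5% at 0.8. At ICC 0.5, simulated power (10,000 runs) falls from 75.5% to 72.5% for 48% against 21%, and from 80.0% to 77.1% for 79% against 50%. Part of that fall only removes the excess rejection of the unadjusted test.
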